1.0 Objectives / Specific Aims

One of the hallmark symptoms of Autism Spectrum Disorder (ASD) is difficulty with social communication and interaction. Although numerous behavioral interventions have been developed to address social difficulties in ASD, one evidence-based social skills training program in particular has demonstrated promise in improving social skills knowledge and social functioning: the UCLA Program for the Education and Enrichment of Relational Skills (PEERS)[1], which is a manualized, evidence-based program for high-functioning adolescents with ASD. Despite the success of this program, not all individuals benefit from social skills training[2]. Reasons for non-responsiveness are likely complex and varied, ranging from differences in neural responsiveness, cognitive function, temperament and social support. One neurocognitive factor that may impact social learning is the ability to filter out irrelevant information, or attend to relevant social information [3]. Therefore, targeting selective attention at the neural level may have benefits for social skills learning. Recently, brain stimulation techniques such as transcranial direct current stimulation (tDCS) and repetitive transcranial magnetic stimulation (rTMS) have shown promise in enhancing learning, attention and other behavioral outcomes in ASD [4-6].

In the present proposal adolescents with ASD who will receive PEERS training with active or sham tDCS to determine whether social skills training can be enhanced with neuromodulation. tDCS is a minimally invasive neuromodulatory technique that delivers low current through scalp electrodes. tDCS modulates ongoing neural activity by affecting neuronal membrane potential. tDCS has shown some promise in reducing neuropathic pain [7], alleviating symptoms in some psychiatric disorders [8-9] and enhancing motor function following stroke [10]. tDCS was chosen as a neuromodulatory technique in the present proposal due to its portability which is well suited to allow for tDCS to be delivered concomitantly with social skills training, which requires interaction with a group of individuals. Animal studies also suggest that the effects of tDCS stimulation may last beyond the period of stimulation [11].

The aims of this study are to:

- **Aim 1.** Establish the safety and feasibility of administering active and sham tDCS with PEERS training in adolescents with ASD. We predict that tDCS administered with 1.5mA current will be safe for participants and tolerable for the majority of participants.
- **Aim 2.** Examine the impact of tDCS in improving social skills and attention to faces. We predict that active tDCS in conjunction with PEERS training will improve social function and attention to faces to a greater degree than sham tDCS plus PEERS training.
- **Aim 3.** Examine the impact of tDCS on neural correlates of social function and attention to faces using functional magnetic resonance imaging (fMRI). We predict that activity in regions that underlie social behavior (e.g., medial prefrontal cortex, temporoparietal junction, fusiform gyrus, amygdala) will increase more in response to social stimuli following active tDCS with PEERS training compared to sham tDCS with PEERS training.

Impact. The present study will address the need to find approaches to enhance social learning in ASD. Social communication difficulties may become especially apparent during adolescence, a time period marked by greater emphasis on social relationships and peer influence. Therefore, the present strategy is to examine the efficacy of a minimally invasive neuromodulatory technique in adolescents in combination with an evidence-based behavioral intervention, PEERS, to enhance social information processing and social interaction, with fMRI markers of neural plasticity before and after intervention.

2.0 Background

PEERS. PEERS is one of the only empirically supported social skills programs for adolescents with ASD. PEERS utilizes cognitive-behavioral methods to teach social skills[12]. The program specifically targets friendship, relationship development, and decreasing isolation in adolescents[13]. The PEERS intervention consists of 14 weekly 90-minute sessions for adolescents and their parents. Four previous randomized, controlled studies and one quasi-experimental study cited gains in overt social skills, improved quality of friendships, and frequency of peer interactions[1, 13-16], with treatment gains maintained at 14-week follow-up[1].

To date, only one study has investigated neural function in a group of adolescents completing the PEERS program[13]. This study demonstrated a shift from right-hemisphere gamma-band EEG asymmetry to left-hemisphere EEG asymmetry following completion of PEERS. No such changes were noted in typically developing adolescents or in wait-listed ASD participants. In addition, left-dominant EEG-asymmetry at post-test was associated with increased social contacts, knowledge about social skills, and fewer symptoms of ASD. The present study has promising implications for demonstrating that cognitive-behavioral intervention is associated with changes in neural activity in adolescents with ASD.

Only two previous studies have investigated the effect of tDCS on children with ASD. Results indicated improved syntax acquisition following a 30-minute treatment period[4] and decreased autism symptoms and behavioral problems up to seven days post-treatment[17]. Both studies reported that treatment was well-tolerated by participants. Recent reviews have also concluded that tDCS is well tolerated and safe for adolescents [18].

Innovation

PI [name] conducted an fMRI study [20] in typical and ASD youth to examine neural response to faces and non-faces. They found that the right fusiform gyrus showed a trend toward normal development of face specialization in ASD (i.e., increased fMRI response to faces relative to non-faces with age), but the left amygdala actually showed decreased face specialization with age in ASD. This finding fits in with the EEG finding that it was left hemisphere gamma activity that was associated with improved social skills in ASD following PEERS training[13] and with the case report that tDCS applied to the left dorsolateral prefrontal cortex decreased ASD symptoms[21]. Hence, left-hemisphere structures may show altered response to social information, but PEERS training, tDCS, or the combination, as proposed here, may mitigate this altered responsivity.

3.0 Intervention to be studied (if applicable)

PEERS training will be paired with active or sham tDCS. As described above, PEERS is one of the only empirically supported social skills programs for adolescents with ASD. PEERS utilizes cognitive-behavioral methods to teach social skills[12]. PEERS is a parent-assisted intervention that teaches targeted social skills to high-functioning patients with ASD during fourteen weekly sessions. Parents and adolescents attend separate concurrent sessions that instruct them on key elements about making and keeping friends. Details of the activities that occur during PEERS sessions are provided in the Section 10.0.

tDCS is a brain stimulation technique that uses 1-2mA current applied to the scalp to affect neuronal membrane potential but does not cause neural firing. It is being explored as a therapeutic for a number of neurological and psychiatric disorders, and appears to be promising in terms of enhancing behavioral or treatment response when administered concurrently with behavioral treatments [22-23]. tDCS is still in the early stages in its application to children, with encouraging initial results across disorders and computational models for dosage considerations in a youth population[24]. Previous research has demonstrated that tDCS is well-tolerated and safe for children and adolescents in a Psychiatry setting [18]. It is also tolerated by children with epilepsy with no adverse side-effects and clinically significant decreases in seizure activity for 48 hours post-treatment [25].

As described more in Section 10.0, active tDCS will be administered to half of the participants and sham tDCS will be administered to the other half

tDCS is not an FDA-indicated technique for autism-spectrum disorders and there are no FDA-approved tDCS devices to date. However the Ionto device used for this study is FDA-approved for iontophoresis and is equipped with all relevant current and voltage regulation/safety features. As with most tDCS studies conducted at MUSC, this device will be used off-label for tDCS delivery.

4.0 Study Endpoints (if applicable)

The primary endpoints are changes in responses on various clinical measures pre- and post-intervention: the Social Responsiveness Scale, the Social Skills Improvement System, the Quality of Play Questionnaire, the Aberrant Behavior Checklist, and the Test of Adolescent Social Skills Knowledge-Revised. We predict that participants receiving active tDCS will show greater improvement in these measures compared to those receiving sham tDCS. This will be assessed using non-parametric t-tests (IBM SPSS Statistics, Chicago, IL) conducted separately for each measure.

Secondary endpoints will be fMRI response and reaction time pre- and post-intervention on a laboratory test of attention and social information processing.

The primary safety endpoint will be self-reported adverse effects of tDCS collected after each treatment session.

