6.0 Number of Subjects

A total of 34 subjects will be recruited for the study (17 adolescents and their parent), but a drop-out rate of approximately 40% is expected, leaving 10 adolescent subjects with complete datasets.

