10.0 Study Design / Methods

We will conduct brain stimulation with 17 randomized adolescent participants at initial enrollment. Drop-outs are expected, with the goal of having 10 youths with ASD complete the study, with the same number of parents actively participating by the end of the experiment.

The following table summarizes the schedule of activities for a subject:

Schedule of events	Activities	Time commitment for volunteer	Compensation
Initial visit with research coordinator, Drs. [name] and [name]	Consent (parent and child)	15 min	\$25 (child) \$15 (parent)
	Medical & MRI screening (parent and child)	5 min	
	ADOS-2 & KBIT-2 (with child), clinical measures (with parent)	90 min	

	Mock scanner training with child	10-15 min	
	fMRI scanning with child	30 min	
	tDCS acclimation with child	10 min	
PEERS weekly sessions	PEERS training plus active / sham tDCS	1 hr / week x 14 weeks	\$15 per session (child) \$0 (parent)
Post-intervention visit	clinical measures (with parent), fMRI scanning (with child)	45 minutes	\$25 (child) \$25 (parent)
14-week follow-up visit	clinical measures completed online (by parent)	30 minutes	\$10 (child) \$50 (parent)

Parents will make initial phone or email contact with the study coordinator. The study coordinator will conduct a brief telephone screening to determine preliminary eligibility for the study. If eligible, the study coordinator will schedule the initial visit.

The initial visit will last approximately 3 hours. Following informed consent (see Section 9.0), an in-depth MRI screening form will be filled out by the parent and the medical history information obtained during the initial telephone interview will be reconfirmed. Any female participants will complete a pregnancy test. [name] will then conduct the ADOS and K-BIT with the child while the parent completes the following clinical outcome measures on a computer (using RedCap) in a separate room: Social Responsiveness Scale-2 [26], the Social Skills Improvement System, the Quality of Play Questionnaire, the Aberrant Behavior Checklist, and the Test of Adolescent Social Skills Knowledge-Revised [27]. The child and parent are given a 10-minute break and a healthy snack, if desired.

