12.0 Data Management

Statistical Power. Schneider and Hopp [4] reported an effect size of 2.87 (Cohen's d) for improvement in syntax acquisition in minimally verbal children with autism following 30 minutes of tDCS. This large effect size requires a minimum sample size of 10 subjects, which is comparable to the proposed sample size. However, that study tested a different domain (syntax acquisition) from the present study (social cognition and communication) and sample of children with higher autism severity. Nevertheless, those initial findings are promising indicators of the efficacy of the use of tDCS in ASD.

Data Analysis plan.

- **AIM 1:** We predict that adverse effects and ratings of discomfort, pain, and side effects will be minimal. Only descriptive statistics will be used – frequency of reports of different types of discomfort or pain.
- **AIM 2:** We predict that participants receiving active tDCS will show greater improvement on the Social Responsiveness Scale, the Social Skills Improvement System, the Quality of Play Questionnaire, the Aberrant Behavior Checklist, and the Test of Adolescent Social Skills Knowledge-Revised compared to those receiving sham tDCS. This will be assessed by examining descriptive statistics for each measure..
- **AIM 3:** We predict that after intervention, all participants will show increased social brain network response to faces (v. objects) and to direct (v. averted gaze), with a greater response in those receiving active tDCS. The analysis of fMRI data will include preprocessing (geometric distortion correction, head motion and slice timing correction, spatial (7-mm FWHM) and temporal high-pass (100 sec cutoff) filtering and spatial normalization to MNI space via each subject's high-resolution T1 MPRAGE image. Eight regions of interest (ROIs) will be defined as 10-mm diameter spheres located in left and right medial prefrontal cortex, left and right temporoparietal junction, left and right fusiform gyrus, left and right amygdala, based on prior studies of face processing. In each ROI, percent signal change for faces v. objects or for direct v. averted gaze will be extracted for each subject and for each time point. The effect of tDCS on fMRI signal will be assessed with descriptive statistics.

13.0 Provisions to Monitor the Data to Ensure the Safety of Subjects (if applicable)

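### Sections 4.0 and 12.0 give different analyses, significance tests and descriptive statistics, for the same active-versus-sham prediction on the five primary measures, and nothing says which governs

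*Combined protocol and SAP*

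**What the plan says.** Section 4.0 opens with "The primary endpoints are changes in responses on various clinical measures pre- and post-intervention" and lists five: the Test of Adolescent Social Skills Knowledge-Revised, the Aberrant Behavior Checklist, the Quality of Play Questionnaire, the Social Skills Improvement System and the Social Responsiveness Scale. It continues "We predict that participants receiving active tDCS will show greater improvement in these measures compared to those receiving sham tDCS" and gives the method as "This will be assessed using non-parametric t-tests (IBM SPSS Statistics, Chicago, IL) conducted separately for each measure".

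Aim 2 of the Data Analysis plan in Section 12.0 repeats the prediction: "We predict that participants receiving active tDCS will show greater improvement on the Social Responsiveness Scale, the Social Skills Improvement System", followed by the other three measures and the sham comparison. Its method is "This will be assessed by examining descriptive statistics for each measure". Aims 1 and 3 in that section are also descriptive.

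The Statistical Power paragraph, also in Section 12.0, takes an effect size of d = 2.87 from a cited tDCS study of syntax acquisition and states "This large effect size requires a minimum sample size of 10 subjects". Section 6.0 plans 17 adolescents and says "a drop-out rate of approximately 40% is expected, leaving 10 adolescent subjects with complete datasets".

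**The concern.** The two sections agree on the arms, the measures and the direction of the prediction, and disagree on how it will be assessed. One promises a test per measure; the other names no test. An analyst could decide after seeing the data whether to report p-values, and either choice would comply with the protocol.

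What is at stake is the kind of conclusion the trial may draw on its primary endpoints. Under Section 12.0 there is no type I error to control, but also no test behind a statement that active tDCS improved more than sham. Under Section 4.0 there are five primary p-values and no rule for reading them together. That section gives no alpha, sidedness, lead measure or multiplicity adjustment, and a non-parametric t-test is not a defined procedure, since a t-test is parametric.

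**Working it through.** **1. The two rules side by side.**

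| | Section 4.0 | Section 12.0, Aim 2 |
|---|---|---|
| Measures | five named | the same five |
| Comparison | active v sham | active v sham |
| Prediction | active improves more | active improves more |
| Method | a separate test per measure | descriptive statistics per measure |

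No section ranks one over the other or calls them complementary, and the documents contain no amendment log that would mark either as superseded.

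**2. The plan's own sample size.** Alpha and power are not stated. Assuming two-sided 0.05 and a two-sample t-test at d = 2.87, noncentral-t power is 0.748 with 3 per arm, 0.919 with 4 and 0.977 with 5. The required total is therefore 8 for 80% or 90% power and 10 for 95%. Dropout: 10/(1 − 0.40) = 16.7, rounded up to 17, which matches enrolment. A minimum of 10 has meaning only for a test, so Section 12.0 does not read as purely descriptive either.

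**3. Consequence if Section 4.0 governs.** Assumptions: exact two-sided Wilcoxon-Mann-Whitney, 0.05 per measure, no ties, 10 completers split 5 v 5.

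- There are C(10,5) = 252 rankings. Attainable two-sided p-values up to 0.05 are 2/252 = 0.0079, 4/252 = 0.0159 and 8/252 = 0.0317; the next is 14/252 = 0.0556. Actual size per test is 0.0317.
- Chance of at least one false positive in five independent tests: 1 − (1 − 0.0317)^5 = 0.149.
- Section 10.0 has one parent complete all five measures ("while the parent completes the following clinical outcome measures on a computer"), so positive correlation is plausible. The documents give no value, so a range is shown, from simulation with five equally correlated normal measures (200,000 runs):

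| Correlation | 0 | 0.3 | 0.5 | 0.7 | 0.9 |
|---|---|---|---|---|---|
| 5 v 5 (size 0.0317) | 0.149 | 0.143 | 0.130 | 0.110 | 0.079 |
| 4 v 6 (size 8/210 = 0.0381) | 0.176 | 0.168 | 0.152 | 0.130 | 0.091 |

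Other readings of Section 4.0, at 5 v 5 with independent measures:

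- One-sided exact test: size 12/252 = 0.0476; familywise 1 − (1 − 0.0476)^5 = 0.22.
- Two-sided normal approximation without continuity correction: size 14/252 = 0.0556; familywise 1 − (1 − 0.0556)^5 = 0.25.

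**4. Cost of a Holm adjustment, two-sided.** The first step is 0.05/5 = 0.01. At 5 v 5 only complete separation of the arms meets it (p = 0.0079). Simulated power per measure, normal equal-variance data:

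| True d | p ≤ 0.05 | p ≤ 0.01 |
|---|---|---|
| 1.0 | 0.21 | 0.07 |
| 2.0 | 0.68 | 0.38 |
| 2.87 | 0.94 | 0.73 |

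At 4 v 6 the smallest p is 2/210 = 0.0095; at 3 v 7 it is 2/120 = 0.0167, so the step cannot be met. If 17 are randomised as 8 and 9 and a random 10 complete, the split is 5 v 5 with probability 56 × 126/19448 = 0.363, 4 v 6 either way with 0.484, and 3 v 7 or more uneven with 0.138 + 0.015 = 0.153.

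**5. Precision under estimation.** The 95% t-interval half-width at 5 v 5 is 2.306 × √(1/5 + 1/5) = 1.46 SD of the change score. The documents give no SD, so it cannot be put in scale points.

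**The case against.** The strongest reply is that Section 12.0 holds the dedicated analysis plan, goes through the aims in order and is descriptive throughout, so the sentence in Section 4.0 is a leftover. The Holm procedure appears as reference 31 but is not cited in the visible text, which fits an inferential plan that was removed. On that reading one stale sentence needs deleting and the multiplicity question disappears. This is plausible, but it is inference: the documents do not say it.

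A weaker reply is that the methods are complementary, because Aim 1 limits itself to descriptive statistics only and Aim 2 omits that limit. It fails because each section presents its method as how the prediction will be assessed.

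Three smaller points are fair. The power paragraph cautions that its effect size comes from a different domain and a more severely affected sample, so it is supporting evidence at most. This is a pilot with feasibility as its first aim, which argues for estimation but does not excuse two plans for the primary endpoints. The error-rate figures describe one version of Section 4.0: one-sided or asymptotic tests give 22% or 25%, so 15% is not an upper bound, and ties would change the exact values. The Holm cost is also specific to two-sided testing. One-sided, the 0.01 step is also met by the second most extreme ranking (2/252 = 0.0079), power there is about 0.13 at d = 1.0 and 0.86 at d = 2.87, and 3 v 7 can reach it (1/120 = 0.0083).

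**Conclusion.** The concern holds and must be fixed. Two current sections state incompatible methods for the same prediction on the primary endpoints, and reading the documents cannot settle which applies. That conclusion rests on the text alone and on none of the calculations.

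The size of the consequence is conditional. Only if Section 4.0 governs, and under the exact two-sided test assumed above, is the familywise false-positive chance about 8% to 15% at 5 v 5 and 9% to 18% at 4 v 6, over correlations from 0.9 down to 0. Other readings of the unnamed test reach about 25% if the measures are independent. If Section 12.0 governs, the consequence is a limit on what may be claimed, not an error rate.

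**What to change.** State one analysis, in the same words, in Section 4.0 and in Aim 2 of Section 12.0, before the blind is lifted. Reconciling the sections is essential; the choice of route is the sponsor's.

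**Preferred, with about 10 completers.** Delete the test sentence from Section 4.0 and write in both places:

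> For each measure we will report the active-minus-sham difference in change from baseline with a 95% confidence interval. This is estimation; no confirmatory claim will be made.

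Reword the sample-size sentence in Section 12.0 so that it no longer implies a test. A Hodges-Lehmann interval would keep the non-parametric choice; its attained coverage at 5 v 5 is 1 − 0.0317 = 96.8%, which should be stated in place of 95%. Baseline adjustment is optional. The cost is that no p-value claim is available and the intervals will be wide.

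**Alternative, if p-values are kept.** In both sections, name the exact Wilcoxon-Mann-Whitney test, alpha and sidedness, and either name one primary measure or apply Holm across the five. Naming one measure avoids the Holm penalty. If Holm is chosen, state its loss of power and that an uneven completer split may put its first step out of reach.

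Either route changes protocol wording only, with no effect on data collection.

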A brief questionnaire about adverse effects will be completed with participants and their parents immediately following the second and last treatment sessions. Tolerance for tDCS will be monitored during tDCS delivery by noting the frequency with which a subject reported irritation, discomfort, burning or pain, whether a subject attempted to remove the tDCS leads, whether a subject wished to discontinue the procedures due to the tDCS (rather than the PEERS training). After the second and last PEERS sessions, the experimenters will administer a brief questionnaire with the subject about whether they felt uncomfortable itching, tingling, burning during the session or whether they have had headaches, neck pain, sleepiness, moodiness in the past week. Any of these effects will be recorded. We will conclude that tDCS can be tolerated if these effects are experienced less than 25% of the time for a given individual. We will also report on how many subjects tolerated the procedures.

The child and parent receive compensation in the form of gift cards following each visit to MUSC (see Table above).

After 14-weeks of PEERS training, subjects will return for a post-treatment session in which the clinical outcome measures will be completed by parents and fMRI session will be completed by the participants (same procedures as before excluding tDCS acclimation).

Finally, 14 weeks after the post-treatment session, the parent will be sent a reminder via RedCap to complete the clinical outcome measures. In addition, both parent and child will be asked to guess which condition the child was assigned to (active or sham tDCS). Once the final follow-up surveys are completed in RedCap, the final gift card of \$75 is mailed to the family.

Information about which condition a subject was assigned to is not typically provided, but if a subject asks, we can tell them after all study procedures are completed and the blind is lifted. Study personnel will also be asked to guess the condition before the study blind is lifted.

Source records: the data collected from subjects include: parental and subject responses on clinical tests and questionnaires, anatomical and functional MRI scans, reaction time and accuracy responses on the fMRI task.

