This project involves both a medical device intervention (tDCS) and a behavioral intervention (PEERS training). fMRI scanning, while not an intervention, will be conducted prior to and following 14-weeks of weekly tDCS sessions.

For tDCS, safety of the participants will be monitored during and immediately after delivery of tDCS to the scalp. During tDCS stimulation, subjects have the option of wearing a ski cap which may reduce discomfort. They will be introduced to the ski cap during the tDCS acclimation session on the initial visit. Some subjects may opt not to wear the ski cap, but it will not affect tDCS delivery. At the end of the sessions that involved tDCS delivery, subjects will be asked if they felt or feel any sensations on the scalp where the electrode was and responses are recorded by the experimenter. In [name] experience and other reports in the literature, any sensations of pain, tingling, itching, stinging or irritation follow the onset of stimulation for about 30-60 seconds and do not persist longer than that. If subjects report feelings of sensation or pain that are unmanageable, a local analgesic cream (benzocaine) can be used or the level of current can be reduced to help them complete the session. [name] will be present during all experimental sessions when tDCS is delivered and will be able to monitor for any adverse medical effects.

Adverse effects will be defined by painful sensations that are unmanageable and cannot be alleviated using the procedures outlined above or by persistent reports of high levels of pain by a participant. Although we do not expect this to occur, such events will be reported to the IRB.

For PEERS training, which is a behavioral intervention, the risks are minimal, but include potential discomfort in interacting with other individuals. Should this intervention prove to be too distressful for an individual, the individual will have the option to discontinue the study. Distress would be indicated by persistent withdrawal from or refusal to engage in PEERS activity, persistent protesting, crying or agitation during PEERS sessions. [name] and the research assistant will make the decision as to whether an individual is experiencing distress. When these behaviors lead to removal from the study, these will be reported as adverse events to the IRB.

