15.0 Risks to Subjects

The risks to the adolescent subjects are as follows:

Participants may feel restless or uncomfortable when lying in the MRI scanner. This may occur and is generally not serious.

Eye strain and dry eyes may occur. This occurs occasionally but is not serious

The MRI scanner produces loud noise. With adequate ear protection provided by the experimenters, this is not a significant risk.

Some participants could experience claustrophobia. This occurs infrequently.

Moving too quickly within the magnetic field can cause dizziness. This occurs occasionally but is not serious.

The presence of metal in the body (excluding dental fillings or some types of permanent retainers) and surgical implants can potentially cause injury when the individual is placed in a strong magnetic field. This occurs very rarely if subjects are well-screened. It is serious.

High-resolution anatomical scans collected for research purposes as part of the study could reveal some type of brain abnormality or pathology. This occurs very rarely and may be serious.

tDCS has been linked to onset of seizures in people with epilepsy, but the likelihood of inducing seizures in people without epilepsy is extremely low.

tDCS may cause itching, tingling, burning and discomfort at the site of delivery on the scalp. Headaches have also been reported.

Some of the activities during PEERS training (e.g., role-playing) may cause mild self-consciousness or embarrassment for some individuals. There is potential loss of privacy due to participating in group discussions.

There is potential loss of confidentiality of research records.

The risks to the parents are as follows:

There is potential loss of confidentiality of research records.

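### The safety endpoint is set for every session, but the adverse-effect questionnaire is scheduled only twice, and the 25% tolerability rule has no stated source or denominator

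*Combined protocol and SAP*

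**What the plan says.** Section 4.0 gives the primary safety endpoint as "self-reported adverse effects of tDCS collected after each treatment session". Section 10.0 pairs tDCS with each of 14 weekly PEERS sessions.

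Section 10.0 then schedules the instrument: "A brief questionnaire about adverse effects will be completed with participants and their parents immediately following the second and last treatment sessions". A later sentence in the same paragraph repeats that timing. The form asks about itching, tingling and burning in the session just finished, and "whether they have had headaches, neck pain, sleepiness, moodiness in the past week".

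The tolerability criterion follows directly: "We will conclude that tDCS can be tolerated if these effects are experienced less than 25% of the time for a given individual". The plan does not say which record this percentage is taken from or what it is a percentage of.

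Two other collections exist. Section 10.0 has staff note, during stimulation, how often local discomfort or pain is reported, any attempt to pull off the leads, and any wish to stop because of tDCS. Section 13.0 adds that at the end of sessions with stimulation "subjects will be asked if they felt or feel any sensations on the scalp where the electrode was", and the answers are recorded.

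The Aim 1 analysis in Section 12.0 is descriptive: "frequency of reports of different types of discomfort or pain".

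**The concern.** The questionnaire, given at 2 of 14 sessions, cannot by itself supply an endpoint set for every session. The per-session records narrow the gap but do not close it. They are directed at what is felt at the electrode site and at behaviour during stimulation. The four past-week effects have no scheduled enquiry after the other 12 sessions. Headache is one of them, and Section 15.0 lists it among the tDCS risks: "Headaches have also been reported".

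The 25% rule is a separate problem. A percentage needs a numerator and a denominator, and neither is fixed. Different readings can class the same adolescent differently, and nothing stops the choice being made after the data are seen.

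Early leavers add to this. Section 6.0 says "a drop-out rate of approximately 40% is expected". Anyone who leaves before the second session never receives the form, and a later leaver may complete it only once.

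Safety and feasibility form Aim 1, in minors, with a device used off-label. What is at stake is whether the reported frequencies and the count of adolescents who tolerated tDCS can be interpreted.

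**Working it through.** **Inputs from the plan.** 14 treatment sessions (Section 10.0 table); questionnaire after 2 of them (Section 10.0); 7 items on the form, 3 about the session and 4 about the past week; threshold below 25% per individual; 17 enrolled and 10 expected to complete (Sections 6.0 and 10.0). The 25% threshold is stated without a derivation, so there is no figure to reproduce.

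**Values the rule can take, by reading.**
- Questionnaire alone, counted per administration: 0/2, 1/2, 2/2 = 0, 50, 100%. Below 25% means no effect on either occasion.
- Questionnaire items pooled: 7 × 2 = 14 answers, so steps of 1/14 = 7.1%.
- All treatment sessions: k/14. 3/14 = 21.4% passes and 4/14 = 28.6% fails, so below 25% means at most 3 sessions.

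**How far the first and third readings differ.** Let p be the chance of an effect at a session, assumed constant and independent across sessions. The documents give no value for p, so a range is shown.
- Two questionnaires: P(tolerated) = (1 − p)².
- Fourteen sessions: P(tolerated) = P(X ≤ 3), with X binomial(14, p).

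| p | 2 questionnaires | 14 sessions |
|---|---|---|
| 0.10 | 81% | 96% |
| 0.20 | 64% | 70% |
| 0.25 | 56% | 52% |
| 0.30 | 49% | 36% |
| 0.50 | 25% | 3% |

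The two-occasion reading is stricter at low rates and more lenient at high rates; the curves cross between 20% and 25%. The extremes for one adolescent are effects at 12 of 14 sessions (86%), sparing only sessions 2 and 14, which gives 0/2 and a pass; and an effect at 1 of 14 (7%) that falls on session 2 or 14, which gives 1/2 = 50% and a fail.

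**Coverage of past-week effects.** Asked straight after sessions 2 and 14, a one-week recall covers the weeks following sessions 1 and 13: 2/14 = 14.3%. At an assumed 10% weekly rate, again independent, the chance of at least one report is 1 − 0.9² = 19% over 2 weeks, against 1 − 0.9¹⁴ = 77% over 14. At 20% it is 36% against 96%.

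**Dropout.** 17 − 10 = 7 adolescents (41%) may have fewer than two questionnaires. The plan does not predict how many would leave because of tDCS. Each one counted as not tolerating moves the rate by 1/17 = 5.9 percentage points.

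**The case against.** Section 4.0 does not name the questionnaire, and Section 13.0 provides a self-report at the end of every stimulation session. For local sensations, then, the endpoint can be supplied as written. This stands, and it is why the gap is confined to the four past-week effects.

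The paragraph that ends in the 25% rule also describes a frequency record kept during stimulation. A rule about how often effects occur fits that record well. A reader might infer that the rule can produce only 0, 50 or 100%. The documents do not support that: it holds only for the questionnaire alone, counted per administration. The wording of the rule follows the questionnaire items, which makes that reading natural, but all-session and item-pooled readings are also open. The ambiguity is the defect.

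Section 13.0 defines adverse effects narrowly, as unmanageable or persistently severe pain. On that definition sleepiness and moodiness fall outside the endpoint. Section 10.0, however, uses the term for a form that includes them, so the narrow definition does not settle the matter.

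A reader might also fault the endpoint for omitting the baseline acclimation ramp. Section 4.0 concerns treatment sessions, and acclimation is not one, so this is not part of the point.

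On early leavers, Section 10.0 already records a wish to stop because of tDCS and promises a count of those who tolerated the procedures. Tolerance information on leavers therefore does not depend on the questionnaire alone. What is missing is a statement of how they enter the count.

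**Conclusion.** The inconsistency in scheduling is real, and it leaves headache, neck pain, sleepiness and moodiness with scheduled enquiry covering about 2 of 14 post-session weeks. The source and denominator of the 25% rule are undefined, and two plausible readings differ by 15 percentage points at a 10% rate and by about 22 at 50%, in opposite directions. Near 20–25% they almost agree. Those probabilities rest on a constant, independent rate that the documents do not supply; they show sensitivity to the reading and do not forecast the trial's results.

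It would go too far to conclude that per-session safety data are absent or that tolerability will be misreported. Local sensations are recorded at each session, and Aim 1 carries no test, power calculation or sample size. This is a minor correction worth considering, made more worthwhile because it concerns safety data in minors and is cheap.

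**What to change.** **Section 10.0.** Give the brief questionnaire after every treatment session, including the last one attended by anyone who leaves early. Compute the 25% rule per adolescent over all treatment sessions attended, and say which reports make a session count. Show the number attended beside each result: with four or fewer sessions a single effect already fails (1/4 = 25%), and with five it passes (1/5 = 20%). Past-week answers at session 1 describe the time before treatment. The week after session 14 is covered only if those four items are also asked at the post-intervention visit.

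**Section 12.0, Aim 1.** Report tolerability over all adolescents who received any treatment session, and count as not tolerating anyone who permanently stops because of tDCS. An adolescent who stops one session and returns, as Section 9.0 allows, is not a failure on that ground.

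**Fallback.** If only two questionnaires are kept, say so in Section 4.0, run the 25% rule on the per-session scalp-sensation record, and report headache, neck pain, sleepiness and moodiness descriptively.

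**Cost.** Changes of wording, plus up to 14 − 2 = 12 more short forms per completer, at sessions where staff already ask and record. The tolerability figure may come out slightly less favourable. No change in design or sample size is needed.
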